Sample size for the study is based on the primary outcome measure of PHQ-8. The difference between the randomized treatment control subjects for the change in score from “Treatment Week 4” versus baseline will be compared with a two-sample t-test at the one-sided 0.025 alpha level. For a planned sample size of 175 total subjects with 1:1 allocation, the study will provide 80% power for an effect size of 0.426 where effect size is based on the ratio of the difference of means over the standard deviation.

p value: two-sample t-test at the one-sided 0.025 alpha level

Statistical Analyses:

Primary analyses of primary and secondary outcome measures will be based on the comparison of the randomized groups via t-tests for means for the change from baseline. Sensitivity analyses for the assumption of normality and for the impact of missing data will be performed. Subgroups results based on sex and race will be provided.

Inclusion/Exclusion

- Age greater than or equal to 21
- US resident
- Can receive packages to their home via UPS/Fedex/USPS
- Major Depressive Disorder
- PHQ-8 Score greater than 10 (show some signs of mild to moderate depression)
- PHQ-8 Score less than 20 (given remote study serious depressed should be excluded)
- Read/write English
- have not contemplated suicide in the past year
- not been institutionalized for mental health issues.
- not currently experiencing problems with alcohol or drug abuse
- can commit to not drinking alcohol 4 hours before bedtime for the duration of the study
- can commit to two (2) 20 minute sessions per day for 8 weeks
- has not used a brain stimulation treatment in one year
- no suspected or known history of heart disease
- no pacemaker
- not under medical supervision for other serious medical condition
- not taking opioids
- are a resident of states in which we have licensed medical professionals
- Any co occurring significant psychiatric disorder that would impair participant's participation
- any use of illicit drugs

Those with a PHQ-8 score greater than 20 will be directed to contact local mental health assistance and will be provided with the National Suicide Prevention Hotline number for immediate assistance.

Recruitment

Individuals in the study will be recruited in two forms targeted to the states in which we have contracted with licensed medical professionals.

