- Fisher Wallace email marketing to patients who have not purchased a Fisher Wallace device and to providers who may refer patients to the study
- Digital advertising on GoodRx, Facebook, Instagram, Google and other common advertising platforms
- Physician referrals.

All potentially interested participants will be directed to the ProofPilot study recruitment page for registration and screening to begin the study.

Study Design/Methods

All participants upon expressing interest, will be asked to create an account on ProofPilot, and answer some basic demographic questions. (Birthdate, location, sex, timezone, preferred language).

All study activities, except those with the Fisher Wallace device itself, will be completed on ProofPilot. ProofPilot is available across any internet connected device with a reasonable screen size. No download is required.

At enrollment, the participant will be asked a series of screening questions, will complete the PHQ-8, the Beck Depression Inventory and a self administered version of the MINI.

Eligible individuals who will be self consented online, will then be asked to take a photograph with their mobile device of a government issued ID for identification. Participants will set an appointment on ProofPilot with a licensed telemedicine psychiatrist in their state within the next several days.

At that virtual visit, the physician will review the participant's responses to the MINI, and add several additional elements that require a physician assessment. Then the physician will administer the HAM-D - and make a final determination if the participant is a good for the study and authorize a prescription for the device.

Participants will then complete additional baseline measures including the QIDS-SR, PROMIS Sleep Disturbance, and Jenkins Sleep Scale. They will then enter in shipping information to place an order for the Fisher Wallace Device.

All participants will be randomized, with a 50/50 chance, into a control arm or active treatment arm. Control arm participants will receive an active treatment device at the end of week 4. This is a double blind design, the participants, nor any study staff, except those conducting fulfillment are aware of which arm the participant is in until unblinding at the end of the study.

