Eligible individuals will then be asked to take a photograph with their mobile device of a government issued ID for identification. They will then enter in shipping information to place an order for the Fisher Wallace Device.

Participants will then complete additional baseline measures including the QIDS-SR, PROMIS Sleep Disturbance, and Jenkins Sleep Scale.

Meanwhile, collected data from PHQ-8, and the Beck Depression Inventory along with proof of identification will be reviewed by medical oversight licensed in the state in which the participant resides and the order released with a prescription for the device. An appointment will be made for the physician to meet with the patient over video telemedicine. During this visit, the physician will evaluate the patient using previously collected baseline data, and their own assessments (MINI, HAM-D) to ensure proper diagnosis and set a professional assessment baseline.

Should the physician feel the participant is a good match, they will issue the prescription for the Fisher Wallace device.

Shipments will be fulfilled by the sponsor's fulfillment capacity by individuals who are not affiliated with the study. All study staff, including remote physicians, will be blinded to who receives the sham and who receives the active device. Tracking information from UPS/Fedex/USPS will trigger tasks based on where the shipment is in the fulfillment process, including at delivery.

At delivery, ProofPilot will automatically trigger instruction tasks, a treatment expectancy survey, and a notification to "Start the trial." The "Start the trial" task will trigger the 2 week, 4 week and 8 week follow up points key to the outcome measures. It will also trigger the window period for the final (week 4) participant/physician video teleconference assessment.

Participants will receive a daily treatment diary at 6:45AM (though they may complete it anytime within an 18 hour period). The daily treatment diary will ask about treatment adherence and any adverse events from the prior day and provide a morning treatment reminder. Participants will also receive an evening

treatment reminder at 7:15PM. Reminders will be presented from ProofPilot in the morning and in the evening adjusted for the participant timezone.

At the end of the study, participants will need to return both the active and sham devices to qualify for compensation.

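### The primary analysis is fixed as an unadjusted t-test on change, although the same-scale baseline is collected and adjusting for it costs almost nothing

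*Protocol*

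**What the plan says.** Under Statistical Analyses, the primary analyses of the primary and secondary outcomes are "based on the comparison of the randomized groups via t-tests for means for the change from baseline". The Sample Size section says that the change to week 4 "will be compared with a two-sample t-test at the one-sided 0.025 alpha level", and a separate line repeats it: "p value: two-sample t-test at the one-sided 0.025 alpha level". The design is "For a planned sample size of 175 total subjects with 1:1 allocation", with 80% power for an effect size of 0.426. No covariate is named, and the only sensitivity analyses mentioned concern normality and missing data.

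The baselines exist. Under Study Design/Methods, participants at enrolment "will complete the PHQ-8, the Beck Depression Inventory and a self administered version of the MINI". The physician visit then uses "their own assessments (MINI, HAM-D) to ensure proper diagnosis and set a professional assessment baseline". Treatment Instructions places randomisation after the prescription, so all three scales are measured before randomisation. The schedule table repeats BDI and PHQ-8 at weeks 2 and 4, and HAM-D at week 4.

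**The concern.** Analysing change from baseline amounts to subtracting the baseline with a coefficient of exactly 1. If the true slope of follow-up on baseline differs from 1, some baseline variation stays in the change score as noise. ANCOVA estimates the slope and removes that noise. With equal allocation this cannot cost precision in large samples, even if the slopes differ between arms.

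The Study Design section intends weeks 1-4 to support a premarket submission, and the trial is sized at 80% power with no margin shown. Information already paid for through the baseline assessments may go unused. The choice also has to be made in advance: an adjusted primary analysis adopted after unblinding would be open to challenge.

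**Working it through.** **Inputs from the protocol.** N = 175, 1:1 (taken as 87 and 88), one-sided alpha 0.025, effect size 0.426. The protocol defines the effect size as the mean difference over the standard deviation. I read that as the SD of the change score, since change is what the test compares.

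**Step 1: the stated power.** The noncentrality is 0.426 / √(1/87 + 1/88) = 2.818. With 173 df, the noncentral t gives power 80.0%. The stated figure is correct for the t-test.

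**Step 2: variance of ANCOVA relative to the change score.** Let k be the week-4/baseline SD ratio before any selection, ρ the correlation, b = ρk the slope (baseline SD set to 1), and u the factor by which selection narrows the baseline SD, with slope and residual variance kept.

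- Residual variance under ANCOVA: k²(1 − ρ²)
- Variance of the change score: k²(1 − ρ²) + (1 − b)²u²
- Ratio: k²(1 − ρ²) / [k²(1 − ρ²) + (1 − b)²u²]

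The ratio never exceeds 1, and equals 1 only when b = 1.

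**Step 3: assumed ranges.** The protocol gives none of these quantities. I take ρ = 0.3 to 0.7, k = 1 to 1.5, and u = 1, 0.7 or 0.5. Narrowing is included because entry is restricted (PHQ-8 above 10, and "PHQ-8 Score less than 20 (given remote study serious depressed should be excluded"), which works against the case for adjustment.

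**Step 4: power of ANCOVA** at 0.426 change-score SDs, with 172 df and the variance multiplied by 1 + 1/171 for the expected cost of chance baseline imbalance.

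Example: ρ = 0.3, k = 1, u = 1 gives 0.91 / (0.91 + 0.49) = 0.65, and power 93.4%.

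| Narrowing u | k = 1 | k = 1.25 | k = 1.5 |
|---|---|---|---|
| 1 (none) | 85.8%–93.4% | 80.5%–88.4% | 79.8%–84.9% |
| 0.7 | 82.9%–88.1% | 80.2%–84.5% | 79.8%–82.5% |
| 0.5 | 81.5%–84.5% | 80.0%–82.3% | 79.8%–81.2% |

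Each cell is the range over ρ from 0.3 to 0.7. In the k = 1.5 column the minimum falls at ρ = 0.667, where b = 1 and there is no true gain. The loss there is 80.0 − 79.8 = 0.2 power points. The gain can also vanish without a slope of 1: ρ = 0.5, k = 1.5, u = 0.5 has slope 0.75 and power 80.1%.

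**Step 5: detectable effect at 80% power.** It is 0.344 at variance ratio 0.65 and 0.427 at ratio 1, against 0.426 for the t-test.

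**Step 6: simulation** (40,000 trials per setting, t-test versus ANCOVA):

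| ρ, k, u | t-test | ANCOVA |
|---|---|---|
| 0.3, 1, 1 | 79.8% | 93.2% |
| 0.5, 1, 0.7 | 80.5% | 85.5% |
| 0.5, 1.25, 0.7 | 79.7% | 81.8% |
| 0.5, 1.5, 0.5 | 80.1% | 80.1% |
| 0.667, 1.5, 0.7 (slope 1) | 80.1% | 80.0% |

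Type I error was 2.3% to 2.5% for both tests. A separate simulation without narrowing, with k = 1 and arm-specific correlations of 0.3 and 0.7, gave a variance ratio of 0.75. Unequal slopes therefore did not remove the gain.

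**The case against.** The strongest reply is that nothing is wrong: the outcome is defined as change, the test of change is valid, and the trial is sized correctly for it. The benefit rests on three parameters that the protocol does not give. The 93.4% figure is a corner that needs equal SDs, correlation 0.3 and no narrowing. On the 27 combinations of ρ = 0.3, 0.5, 0.7 with the three values each of k and u, 17 give less than 83% and the median is 82.3%. Among the 18 narrowed combinations the median is 81.7%. These combinations are not probabilities, but they show that a small gain is quite possible.

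All of that stands. It limits the size of the claim but does not reverse it, because the downside is about 0.2 points.

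Two further caveats stand. The narrowing model suits PHQ-8, on which entry is directly restricted. BDI has no direct limit, so holding its slope fixed under indirect selection is an extra assumption. The guarantee also relies on near-equal arms among those analysed, and unequal dropout combined with unequal slopes would weaken it.

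That an unseen analysis plan might settle the matter does not remove the point. The protocol does not leave the method open: it names the t-test as primary, and a plan naming another test would contradict it.

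**Conclusion.** The concern holds as a matter of efficiency. The protocol fixes a valid but potentially less precise primary analysis while collecting the covariate that could improve it. The size of the gain is undetermined. Under the assumed ranges, power goes from 80.0% to between 79.8% and 93.4%, with the larger gains confined to low slopes and little narrowing of the baseline. This rests on reading the effect size as change-score SDs, on 1:1 allocation among those analysed, and on the assumed correlations, SD ratios and narrowing.

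The conclusion is the same whether the primary outcome is BDI, as listed under Primary Outcome Measures, or PHQ-8, as named under Sample Size. It does not extend to the delayed-arm BDI change from week 4 to week 8, which is not a comparison of arms, or to SAFTEE. The change should be made, but the trial is not invalid without it.

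**What to change.** Make the primary analysis an ANCOVA of the week-4 score (or, equivalently for the treatment effect, its change) on randomised arm and the same-scale baseline, tested at one-sided 0.025. Use the same model for the between-arm BDI, PHQ-8 and HAM-D secondary outcomes at their stated weeks. Keep the unadjusted t-test on change as a sensitivity analysis, and leave N at 175.

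Edit three places together so that they agree:

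1. Statistical Analyses: name the ANCOVA and its covariate.
2. The p value line: replace the two-sample t-test with the ANCOVA at one-sided 0.025.
3. The sample-size sentence: say that the two-sample t-test is the basis of the power calculation only.

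Any analysis plan needs matching text. The cost is these edits and one degree of freedom; no new data or participants are needed.

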Neurostimulation & Depression Study

Protocol Summary Document for ProofPilot Remote Studies

ProofPilot Study ID:2518

Principal Investigator

[name]

Study Purpose

Examine the safety and effectiveness of the Fisher Wallace Cranial Electrotherapy Stimulator Device on Major Depressive Disorder using two 20-minute per day treatment sessions over eight weeks.

Study Design

This is a fully remote trial where participants engage at home in the study using the ProofPilot study platform. All potential participant enrollment data, including proof of identity via government ID will be reviewed by licensed medical professionals in the participant's state prior to their full enrollment.

Participants will be randomized into an immediate or delayed treatment arm. The immediate treatment arm participants will be shipped an active Fisher Wallace device limited to Level 2 output even if a participant raises the dial beyond that. The participant will remain with the active device for the full 8 weeks.

In the delayed treatment arm, the participants will receive a sham device that looks exactly the same, but only provides treatment for 2 seconds. At week 4, sham arm participants will be unblinded and shipped an active device (limited to Level 2 output even if a participant raises the dial beyond that). The delayed arm participants will continue with active devices for the remaining 4 weeks of the trial.

Physicians, via a telemedicine visit, will diagnose participants, prescribe the device and provide medical oversight. Participants will self-report adherence and any adverse events on a daily basis through diaries. Self-report outcomes will be collected via online assessments at baseline, 2-week point, 4-week point and 8 week points. In addition, physicians will also conduct an assessment at baseline and week 4.

Weeks 1-4 of this protocol are intended to provide sufficient evidence of safety and effectiveness to support the FDA Premarket approval submission for the Fisher Wallace CES device. Data collected in weeks 5-8 of this protocol, relevant to an ongoing evaluation of safety and effectiveness, may be submitted to FDA in the form of an update report, in accordance with 21 CFR § 814.20(b)(13)(e).

Treatment Instructions

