After receiving a prescription via remote asynchronous telemedicine, the patient is randomized to either an immediate or delayed treatment arm, and delivery of the Fisher Wallace device will be made by UPS/Fedex/UPS. Upon delivery (as identified by shipment tracking code), individuals will be presented with video how-to instructions, and treatment overviews (along with some device usage troubleshooting facts). The device packaging will also include instructions. A PDF version of the instructions, along with FAQs will be made available via ProofPilot for quick reference.

Participants will be directed to use the device twice per day for 20 minutes, once soon after waking up, and the second time per day 20 minutes prior to attempting sleep.

The study timeline will commence upon completion of the first treatment as identified by the participant in ProofPilot.

Participants who have questions about the device will be referred to ProofPilot customer support. All queries will be logged and reported at the end of the study. ProofPilot will refer those questions that can not be answered with an automated frequently asked questions system to PI [name] and/or the manufacturer (Fisher Wallace) for follow-up.

Primary Outcome Measures:

- Change in Beck Depression Inventory Score in “Treatment week 4” versus Baseline in immediate versus delayed arm.

Secondary Outcome Measures:

- Change in Hamilton Depression Rating Scale from Baseline to “Treatment week 4” in immediate versus delayed arm.
- Change in Beck Depression Inventory Score in “Treatment week 2” versus Baseline in immediate versus delayed arm.
- Change in Patient Health Questionnaire - 8 (PHQ-8) score at “Treatment week 4” versus Baseline in immediate versus delayed treatment arm.
- Change in Patient Health Questionnaire - 8 (PHQ-8) score at “Treatment week 2” versus Baseline in immediate versus delayed treatment arm
- Change in Beck Depression Inventory Score from “Treatment Week 4” to “Treatment week 8” in delayed treatment arm (once they have started use of the actual device).
- Device safety, tolerability and adherence over 8 week period as measured by SAFTEE

Sample Size:

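### The one-year limit on brain stimulation is a washout: it admits former users and owners of a cranial stimulator, for whom a 2-second sham can compromise the blind

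*Protocol*

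**What the plan says.** - **Eligibility** (Protocol, Inclusion/Exclusion): the participant "has not used a brain stimulation treatment in one year". The list sets no limit on earlier use and does not mention ownership.
- **Sham** (Protocol, Study Design): control participants get "a sham device that looks exactly the same, but only provides treatment for 2 seconds". They receive an active device at week 4.
- **Sessions** (Protocol, Treatment Instructions): "Participants will be directed to use the device twice per day for 20 minutes".
- **Active unit** (Protocol, Study Design): participants are "shipped an active Fisher Wallace device limited to Level 2 output even if a participant raises the dial beyond that".
- **Recruitment** (Protocol, Recruitment): one channel is "Fisher Wallace email marketing to patients who have not purchased a Fisher Wallace device". The others are "Digital advertising on GoodRx, Facebook, Instagram, Google and other common advertising platforms" and physician referrals, neither with a stated restriction on purchase or use.
- **Blinding** (Protocol, Study Design/Methods): "This is a double blind design".
- **Outcome** (Protocol, Primary Outcome Measures): change in Beck Depression Inventory score at week 4, a self-report scale. The Sample Size section names the PHQ-8 as primary instead. That too is self-reported, so this point is the same under either reading.

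**The concern.** A one-year limit deals with carry-over of an earlier treatment effect. It does not deal with two other consequences of earlier experience.

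1. **Recognition.** Someone who remembers a real session has a reference against which to judge a unit that stops after 2 seconds. A participant who works out the arm brings expectancy into a self-reported score. The week 4 comparison cannot separate that from a device effect.
2. **Own unit.** A former user may still have a working stimulator at home. Used while assigned to sham, it would bring active treatment into the control arm and dilute the contrast.

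The Study Design section says that weeks 1-4 are meant to support a premarket approval submission, so the credibility of the blind over those four weeks matters. Eligibility is fixed in the protocol, and an analysis plan that is not shown would not change who may enter.

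**Working it through.** **Who gets through.** A person who last used a cranial stimulator 13 months ago meets the criterion, and so does an owner who has not used the unit for a year. The non-purchaser restriction covers one channel (emails to patients) and one brand, and it concerns purchase rather than use. It is not repeated as an eligibility criterion. A person reached by advertising or referral does not meet it.

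**What might catch it later.** The daily diary is described as covering adherence and adverse events. The expectancy survey is triggered at delivery, before the first session, so it cannot show recognition gained through use. By week 4 a fully adherent participant has had 2 x 28 = 56 sessions.

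**The plan's own figure.** Inputs from the Sample Size section: standardised effect 0.426, one-sided alpha 0.025, power 80%, 1:1 allocation, 175 in total.
- Normal approximation: n per arm = 2 x (1.960 + 0.842)^2 / 0.426^2 = 86.5, rounded up to 87, or 174 in total.
- Exact two-sample t-test: 87.5 per arm, 175 in total, power 80.0%.

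The stated size reproduces. At 87.5 per arm the standard error of the difference in SD units is sqrt(2/87.5) = 0.1512, and the normal approximation gives power 80.4%.

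**(a) Recognition, with no true effect.** Assume that a share f of participants identify their arm and that this shifts the between-arm difference among them by b SD. The overall bias is f x b, and one-sided error = 1 - Phi(1.960 - f x b / 0.1512). Both f and b are assumptions.

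| f | b (SD) | bias (SD) | one-sided error |
|---|---|---|---|
| 2% | 0.25 | 0.005 | 2.7% |
| 5% | 0.25 | 0.0125 | 3.0% |
| 5% | 0.5 | 0.025 | 3.6% |
| 10% | 0.5 | 0.05 | 5.2% |
| 20% | 0.5 | 0.10 | 9.7% |

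**(b) Own active unit in the sham arm, with the planned effect true.** Assume that a share f of the sham arm uses its own unit and gets the full effect. The contrast becomes 0.426 x (1 - f), and power = Phi(0.426 x (1 - f) / 0.1512 - 1.960).

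| f of sham arm | contrast (SD) | power |
|---|---|---|
| 0% | 0.426 | 80.4% |
| 2% | 0.417 | 78.9% |
| 5% | 0.405 | 76.3% |
| 10% | 0.383 | 71.8% |
| 20% | 0.341 | 61.6% |

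If the device works, the two mechanisms pull in opposite directions, so the net effect on the estimate is unknown.

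**The case against.** The strongest reply is that every step after eligibility is inference.

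- **Perceptibility.** The protocol does not say whether Level 2 output can be felt after the first seconds, or how an earlier or different device felt. A reader might infer that any former user can tell the arms apart, so that blinding fails for them. The documents do not support that. They support only that the blind can be compromised. This objection stands.
- **Own unit.** A person would have to own a unit, leave it unused for a year, and then take it up again during a trial that supplies a device and promises an active one at week 4. Nothing in the documents suggests that this is common. It remains possible, and no criterion prevents it.
- **Size.** The shares and shifts are assumed. At a 2% share and a 0.25 SD shift the error is 2.7%, which is negligible. Inputs of 20% and 1.0 SD would give about 26%, but a 1.0 SD shift is more than twice the planned effect (1.0 / 0.426 = 2.3), and nothing in the documents supports that corner. The email restriction also makes a high share of owners of this device less likely from that channel.
- **Repair afterwards.** A reader might infer that the bias could never be corrected. That goes too far: if earlier use were recorded at screening, an analysis without these participants would be possible. The protocol does not itemise its screening questions.
- **Root cause.** A 2-second sham may be recognisable to device-naive participants too, and a tighter criterion does not cure that. This stands as a limit on what the fix achieves.
- **Design preference.** A one-year window contradicts nothing in the protocol. That is true. The case rests on a cheap reduction of a bias risk, not on an internal error.

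**Conclusion.** The point holds as an avoidable weakness in eligibility. The criterion is a washout that admits former users and owners of this or a similar device into a double-blind trial with a 2-second sham and a self-reported primary outcome. The only related safeguard covers a single recruitment channel.

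The size cannot be fixed from the documents. Over the assumed range it runs from negligible (2.7% error, or 78.9% power, at a 2% share) to material at shares of about 10% or more (5.2% error with a 0.5 SD shift, or 71.8% power). These figures rest on assumed shares, on assumed shifts of 0.25 to 0.5 SD, and on full benefit from a privately owned unit.

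The documents do not show that the blind fails for these participants, or that any of them would enrol in numbers.

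**What to change.** Keep the one-year limit for other forms of brain stimulation. Add one criterion that applies to every recruitment channel, for example: *has never used, and does not own, a cranial electrotherapy stimulation device*. Ask it as one item in the ProofPilot screening questions.

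The restriction is confined to cranial electrotherapy because nothing in the documents suggests that experience of other modalities would reveal this sham. The email restriction describes a mailing audience. It should not be read as an existing check of applicants against purchaser records, and such a check would be a new procedure.

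**Cost:** one added criterion and one question, with no change in sample size. The eligible pool becomes somewhat smaller, the answer relies on self-report in a remote trial, and there will be no data on former users. The blind for device-naive participants remains as good or as weak as the sham itself.

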- **Promis Sleep Disturbance:** The PROMIS-SD had greater measurement precision than the Pittsburgh Sleep Quality Index (PSQI) and the Epworth Sleepiness Scale (ESS) as indicated by larger test information values across the continuum of severity, despite having fewer total items, a major advantage for both research and clinical settings.³
- **COMBINE SAFTEE** (systematic assessment for treatment of emergent events modified for mental health and substance abuse)

The blue bar indicates shipment/delivery of the active or sham device.

¹ Kroenke, Kurt; Spitzer, Robert L; Williams, Janet B W (2017-05-31). "The PHQ-9". Journal of General Internal Medicine. 16 (9): 606–613. doi:10.1046/j.1525-1497.2001.016009606.x. ISSN 0884-8734. PMC 1495268. PMID 11556941

² Löwe, Burnd; Spitzer; Gräfe; Kroenke; Quenter; Zipfel; Buchholz; Witte; Herzog (February 2004). "Comparative validity of three screening questionnaires for DSM-IV depressive disorders and physicians' diagnoses". Journal of Affective Disorders. 78 (2): 131–140. doi:10.1016/s0165-0327(02)00237-9. PMID 14706723.

³ A. John Rush, Ira H. Bernstein Development of short forms from the PROMISTM sleep disturbance and Sleep-Related Impairment item banks, Behav Sleep Med. 2011 Dec 28; 10(1): 6–24. doi: 10.1080/15402002.2012.636266 PMCID: PMC3261577 NIHMSID: NIHMS335121 PMID: 22250775

	Enroll	Baseline		2-Week	4-Week	8 Week
Inclusion/Exclusion	X					
Consent						
PHQ-8	X			X	X	X
Beck Depression Inventory	X			X	X	X
M.I.N.I Screen	X					
HAM-D	X				X	
Physician Telemedicine Visit	X				X	
Randomization	X					
Treatment Expectancy			X			
Instructions			X			
Quick Inventory of Depressive Symptomatology (QIDS-SR)		X		X	X	X
Jenkins Sleep Scale		X			X	X
Promis Sleep Disturbance		X		X	X	X
COMBINE SAFTEE				X	X	X
Final Feedback & Tolerability						X
Daily treatment adherence and adverse events						

Adverse Event Reporting & Medical Oversight

Licensed medical providers in the state in which the participant lives will provide medical oversight for this effort.

Adverse events will be collected qualitatively via customer support in the ProofPilot platform. In addition, medical oversight staff will automatically receive alerts if participants have a PHQ-8 score over 20 at the 2 week, 4 week or 8 week point. Those participants will also receive notifications to contact local medical support.

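### An applicant scoring exactly 20 on the PHQ-8 is excluded as too depressed for a remote trial, but the written referral rule starts only above 20

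*Protocol*

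**What the plan says.** The Inclusion/Exclusion section of the protocol sets a lower and an upper PHQ-8 limit. The lower is "PHQ-8 Score greater than 10 (show some signs of mild to moderate depression"). The upper, which comes with its reason, is "PHQ-8 Score less than 20 (given remote study serious depressed should be excluded"). Below the list of criteria is the referral rule: "Those with a PHQ-8 score greater than 20 will be directed to contact local mental health assistance". The same sentence gives those people a national suicide prevention hotline number.

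Three other places bear on what happens to an applicant or participant with a high score:

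- **Study Design** provides for a clinical review before full enrollment: "All potential participant enrollment data, including proof of identity via government ID will be reviewed by licensed medical professionals".
- **Study Design/Methods** has the PHQ-8 completed at enrollment. It then describes consent, the identity photograph and the psychiatrist visit: "Eligible individuals who will be self consented online, will then be asked to take a photograph", followed by "Participants will set an appointment on ProofPilot with a licensed telemedicine psychiatrist in their state within the next several days".
- **Adverse Event Reporting & Medical Oversight** sets an alert during the study: "medical oversight staff will automatically receive alerts if participants have a PHQ-8 score over 20 at the 2 week, 4 week or 8 week point". People who trigger it are also told to contact local medical support.

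**The concern.** The upper eligibility limit and the referral rule address the same group: people whose depression is too severe for a trial run entirely at a distance. One would expect everyone excluded on that ground to be referred. Instead, eligibility stops below 20 and referral starts above 20, so the value 20 belongs to neither rule.

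What is at stake is the care of an applicant, not the inference. The protocol itself judges a person scoring 20 too depressed to take part, yet prescribes neither advice to seek local help nor the hotline number for that person. Screening is done on an online platform, so the written cut-off may well be the one that is configured. That is an inference, because the screening logic is not shown.

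**Working it through.** There is no calculated figure in the plan to reproduce on this point. The check is a comparison of two stated cut-offs.

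**Inputs, all from Inclusion/Exclusion**

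- Eligible on PHQ-8: 10 < score < 20.
- Excluded for severity: score ≥ 20, the complement of the upper limit.
- Referred: score > 20.

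**Assumption.** Scores are whole numbers. The protocol does not say so. The check was run over 0 to 24, but the result does not depend on the top of that range.

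**Step 1: apply the rules as written**

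| PHQ-8 score | Eligible on PHQ-8? | Excluded for severity? | Referral prescribed? |
|---|---|---|---|
| 10 | No (too low) | No | No |
| 11 to 19 (9 values) | Yes | No | No |
| 20 | No | Yes | **No** |
| 21 and above | No | Yes | Yes |

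Excluded for severity but not referred: {score ≥ 20} minus {score > 20} = {20}, one value.

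**Step 2: look for another provision that reaches this applicant**

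- *Clinical review of enrollment data (Study Design).* It covers all potential participants, but no duty to refer those turned away is attached to it.
- *Psychiatrist visit (Study Design/Methods).* It follows for eligible individuals. A score of 20 is not eligible, so the text gives this applicant no route to the visit.
- *Medical oversight of PHQ-8 and Beck scores (later in Study Design/Methods).* Its stated purpose is to release the device order with a prescription. It also follows a step for eligible individuals and mentions no referral.
- *On-study alert (Adverse Event Reporting & Medical Oversight).* It applies to participants at weeks 2, 4 and 8, after enrollment, and it too starts above 20.

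None of the four closes the gap.

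**Step 3: apply the corrected rule**

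With referral at score ≥ 20: {score ≥ 20} minus {score ≥ 20} = the empty set. No one excluded for a high PHQ-8 score is left without a referral.

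**The case against.** The strongest reply is that the two cut-offs need not match. One governs eligibility and the other triggers clinical action. The protocol also uses above 20 for action a second time, in the on-study alert, so the referral threshold may be deliberate. The text does not rule this out, but the reading is weak at screening. The reason given for excluding a score of 20 is serious depression, which is also the evident reason for the referral. If the wording was only loose, the edit records the intent. The same list uses an inclusive limit for age, so the distinction was available to the authors.

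A second reply is that the document is a summary, the screening logic is not shown, and staff might refer such an applicant anyway. This stands as a limit on the claim. What is shown is that the text prescribes no referral at 20, not that anyone would be turned away without help.

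A third is that recent suicidal thoughts are a separate exclusion, so the PHQ-8 limit is not the only severity screen. That is true, but it gives little reassurance here because the text attaches no referral to that exclusion either. For the same reason, the edit proposed here completes the rule only for exclusions by PHQ-8 score.

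Finally, the point may be called too small to raise. Its size is not in dispute. It is still an action threshold that the protocol sets one point away from its own exclusion limit, and not detail left for an analysis plan.

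**Conclusion.** The concern holds, as a minor point. On whole-number scores, exactly one value, 20, is excluded for severity without a prescribed referral, and no other section of the protocol covers that applicant. The finding rests on the whole-number assumption and on the written text alone.

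The effect is confined to screening. Enrollment requires a score below 20, so none of the planned 175 participants is affected, and the estimand, power, randomization and primary analysis are unchanged. How many applicants would score 20 cannot be estimated from the document.

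**What to change.** In Inclusion/Exclusion, start the referral rule at a PHQ-8 score of 20 or greater, and confirm that the screening logic on the study platform uses the same cut-off.

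As an option, and not to correct an error, the sponsor's clinicians may also set the on-study alert at 20 or greater. A participant who worsens to the trial's own exclusion level would then be flagged.

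The cost is a few words of protocol text, a check of the screening logic and a few more referral messages. If the option is taken, there will also be a few more alerts to review.
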